10.2.2 Power Consideration

For the outcome lack of response, 24 samples gathered during years 1-2 provide 80% power to detect a minimum mean difference at baseline of 1.2 (or 1.5) standard deviation between the NR group vs all others (Response group, R), using a two-sided t-test with a significance level 0.5, assuming 50% (or 20%) response rate. Due to the exploratory nature of this aim, the type I error rate will not be adjusted for exploring multiple biomarkers.

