1.4 Hypothesis

Enzalutamide with fulvestrant, by blocking both AR and ER signaling, will synergize in patients with ER+ AR+ metastatic breast cancer. It may prevent AR from taking over from ER when ER signaling is blocked. The extent of AR expression that correlates with enzalutamide efficacy is unknown and is an objective of this study; therefore, all patients, including those with “AR-negative” breast cancer (although this is expected to be fewer than 10%), will be enrolled to receive standard of care fulvestrant with enzalutamide. We hypothesize that 1) AR localization (a shift from nuclear to cytoplasmic) when comparing the pretreatment to the ~4 week tissues will represent a pharmacodynamics (PD) marker of enzalutamide activity. In tumors that respond to treatment, we would not only expect such a shift in AR localization, but also 2) a reduced expression in AR-regulated genes as well as subsequent changes in downstream processes. Thus, comparison of pre- vs during treatment tissues should allow us to identify PD markers as well as predictive biomarkers that indicate no response to enzalutamide (such as no

change in Ki67 or TUNEL). We will be able to measure Ki67 using standard IHC assays as well as a quantitative measurement by Reverse Phase Protein Microarray (RPMA). Multivariate analysis will be required to attempt to classify protein, gene, or TUNEL markers associated with PFS as predictive (of therapeutic impact), prognostic (of intrinsic tumor biology), or mixed as discussed above. A similar plan to compare the preclinical with the clinical analyses should facilitate the discovery and validation of putative biomarkers. The evaluation of Ki67 and TUNEL will provide the preliminary data necessary to mount our preoperative trial proposed in Years 3-5. Sample size and power consideration: 24 baseline samples will provide 80% power to detect a mean difference in change (baseline-during treatment) of 1 (or 1.3) standard deviation between the two groups (NR vs R) using one-sided 2-group t-test with a significance level of 0.05, assuming the response is 50% (or 20%). Statistical analysis plan: the same analysis approaches described in aim 1 will be used here, with the changes (baseline –during treatment) instead of the baseline values. Coefficient variation (CV) will be calculated for each potential biomarkers and biomarkers with smaller CV will be particularly interesting.

2. OBJECTIVES AND OUTCOMES:

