10.2 Sample Size

10.2.1 Determination of Sample Size

The primary outcome is the clinical benefit rate. Assuming the undesirable rate of 10% and desirable rate of 30%, a sample size of 24 provides 89% power to detect this 25% rate difference using an exact binomial test with a one-sided alpha of 0.085. If 5 or more patients show clinical benefit the drug combination warrants further evaluation. During treatment period, patients might withdraw due to toxicity or loss to follow-up before on treatment for 24 weeks. Table below summarize the statistical power and the decision rule for sample size from 24 to 20, a 20% loss in the total sample size, which is the upper bound for loss seen in practice.

Statistical Power	n	Actual Alpha	Reject H0 If R ≥
0.89	24	0.085	5
0.86	23	0.073	5
0.84	22	0.062	5
0.80	21	0.052	5
0.76	20	0.043	5

R is the response as the clinical benefit

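### Three planning figures in section 10.2 are misprinted (a test level of 0.5, a 25% rate difference, a 20% loss); the design itself is unaffected

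*Combined protocol and SAP*

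**What the plan says.** Section 10.2.2 (Power Consideration) covers the comparison of baseline biomarkers between non-responders (NR) and all other patients. With 24 samples it claims 80% power, and it gives the effect as "minimum mean difference at baseline of 1.2 (or 1.5) standard deviation between the NR group vs all others". The test behind that claim is specified in these words: "using a two-sided t-test with a significance level 0.5, assuming 50% (or 20%) response rate". It adds that the type I error will not be adjusted across biomarkers because the aim is exploratory.

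Section 1.4 (Hypothesis) has a related power statement for the change from baseline to on-treatment. It gives 80% power for 1 (or 1.3) SD with a one-sided t-test at 0.05, under the same 50% (or 20%) response assumptions.

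Section 10.2.1 (Determination of Sample Size) covers the primary endpoint. It begins "Assuming the undesirable rate of 10% and desirable rate of 30" per cent, and the same sentence continues: "a sample size of 24 provides 89% power to detect this 25% rate difference using an exact binomial test with a one-sided alpha of 0.085". The combination merits further study if 5 or more patients show clinical benefit. To allow for withdrawals, a table lists power, actual alpha and the threshold, and its range is described as "sample size from 24 to 20, a 20% loss in the total sample size, which is the upper bound for loss seen in practice". Its rows are n = 24, 23, 22, 21 and 20, all with the threshold of 5.

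**The concern.** Each of the three figures conflicts with numbers printed beside it.

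- **Test level.** A two-sided level of 0.5 would flag, on average, half of all biomarkers with no true difference. Because 10.2.2 waives multiplicity adjustment, the per-marker level is the only error control stated for this aim, so the numeral matters even though the aim is exploratory.
- **Primary effect size.** The sentence gives both rates and then a difference that does not follow from them. This is the planned effect for the primary endpoint, so a reader should not have to work out which number was used.
- **Loss to withdrawal.** The percentage attached to the table's range is wrong. That raises the question of whether the table covers the loss it is meant to cover.

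**Working it through.** **1. Test level in 10.2.2**

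Inputs from 10.2.2: 24 samples, a two-sided two-sample t-test, 1.2 SD at 50% response and 1.5 SD at 20% response. A 50% response rate splits the sample 12 and 12. A 20% rate gives 24 × 0.2 = 4.8, so about 5 and 19.

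The noncentrality is d / √(1/n1 + 1/n2), with 22 degrees of freedom. Power is the probability that a noncentral t exceeds the two-sided critical value in either direction. The critical value is 2.074 at 0.05 and 0.686 at 0.5.

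- 12 and 12, d = 1.2: 1.2 / √(1/12 + 1/12) = 2.939
- 5 and 19, d = 1.5: 1.5 / √(1/5 + 1/19) = 2.984
- 4.8 and 19.2 (unrounded), d = 1.5: 2.939

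| Split | Difference | Power at 0.05 | Power at 0.5 | SD detectable with 80% power, 0.05 | Same, 0.5 |
|---|---|---|---|---|---|
| 12 / 12 | 1.2 SD | 0.802 | 0.988 | 1.20 | 0.60 |
| 5 / 19 | 1.5 SD | 0.814 | 0.989 | 1.47 | 0.74 |
| 4.8 / 19.2 | 1.5 SD | 0.802 | 0.988 | 1.50 | 0.75 |

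The plan's 80% at 1.2 and 1.5 SD reproduces at two-sided 0.05. At 0.5 the detectable differences would be about half those printed. Rounding the smaller group down to 4 (4 and 20) gives 0.745 at 0.05 and 0.980 at 0.5, so the choice of split does not rescue 0.5.

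The figures in 1.4 are a separate calculation. At one-sided 0.05 the differences detectable with 80% power are 1.048 SD (12 and 12) and 1.29 SD (5 and 19), which round to the printed 1 and 1.3.

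**2. Rate difference in 10.2.1**

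Inputs from 10.2.1: null rate 10%, target rate 30%, success if R ≥ 5. Alpha is P(R ≥ 5) when R is binomial with n and 0.10. Power is the same probability at 0.30.

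| n | Alpha, computed | Alpha, printed | Power, computed | Power, printed |
|---|---|---|---|---|
| 24 | 0.0851 | 0.085 | 0.889 | 0.89 |
| 23 | 0.0731 | 0.073 | 0.864 | 0.86 |
| 22 | 0.0621 | 0.062 | 0.835 | 0.84 |
| 21 | 0.0522 | 0.052 | 0.802 | 0.80 |
| 20 | 0.0432 | 0.043 | 0.762 | 0.76 |

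All five rows reproduce (at n = 22 the unrounded power is 0.83545, hence 0.84). The difference used is 30 − 10 = 20 percentage points.

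A true 25-point difference does not fit at n = 24. With 10% versus 35%, power would be 0.958 instead of 0.89. With 5% versus 30%, alpha would be 0.006 instead of 0.085.

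**3. Loss in 10.2.1**

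- From 24 to 20: (24 − 20) / 24 = 4/24 = 16.7%.
- 20% of 24 is 4.8 patients, so the largest whole number of patients within a 20% bound is 4, which leaves n = 20.
- Losing 5 leaves n = 19 and is 5/24 = 20.8%, which is outside the bound.

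The percentage is therefore wrong, but the last printed row is the smallest sample within a 20% bound.

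**The case against.** The strongest reply is that these are evident slips with nothing resting on them. The 0.5 looks like a dropped zero, recoverable from the SD figures, and it is a planning input for an exploratory aim. The 30% target stands in the same sentence as the wrong difference, and no test or rule uses 25%. All of this is right, and it limits the point to minor. It does not remove the point: the printed level and the printed difference are contradicted by their own neighbours, and section 10.2 is where an analyst would look for both.

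It is also fair to say that section 1.4 is weak evidence for the intended level in 10.2.2. Its test is one-sided, it concerns change from baseline, and its effect sizes differ. It supports the numeral 0.05 and no more. The case for two-sided 0.05 rests on the power figures in 10.2.2 itself.

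A reader might infer three stronger things, which the documents do not support:

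- **That the power table stops one row short of the worst expected loss.** The plan calls 20% an upper bound. Since 24 × 0.8 = 19.2, a sample within the bound has at least 20 patients. A row for 19 would lie outside it.
- **That the primary target is really 35%.** The stated 30% and all five table rows rule this out.
- **That biomarkers are meant to be tested at 0.5.** The power figures printed in the same sentence do not hold at that level.

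**Conclusion.** All three figures are misstated as printed, and the documents' own numbers show what the calculations used. In 10.2.2 the level must be two-sided 0.05 for the stated 80% power to hold (0.802 at 1.2 SD, 0.80 to 0.81 at 1.5 SD, against about 0.99 at 0.5). In 10.2.1 the difference is 20 percentage points, not 25, and the loss from 24 to 20 is 16.7%, not 20%.

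The sample size of 24, the threshold of 5, and the tabulated alpha and power do not change. Power at the largest whole-patient loss within 20% remains 0.76. The severity is minor; the test level matters most of the three because it is an error rate.

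The result assumes an equal-variance two-sample t-test, group sizes of 12 and 12 or about 5 and 19, and exact binomial tails. It checks the arithmetic of the table rows only, not which patients will be counted in n.

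**What to change.** Three text edits:

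1. In 10.2.2, change the significance level from 0.5 to 0.05, keeping the test two-sided.
2. In 10.2.1, replace the 25% rate difference with *20 percentage-point difference*.
3. In 10.2.1, describe the range from 24 to 20 either as *a loss of about 17%* or as *the largest whole-patient loss within a 20% bound*, whichever the team means.

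No table row needs to be added or recomputed. The cost is wording only: no extra patients, and no change to the sample size or the decision rule.

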10.3 Research Laboratory Data

AR IHC quantitation, AR pathway activation, AR localization (nuclear/cytoplasmic), Ki67 and response, cleaved caspase 3, AR mRNA, AR mutational status, AR splice variants, ER IHC quantitation, ER mRNA, RNAseq, whole exome sequencing, proteomic analysis.

10.4 Research (Statistical) Methods

Data collected in this study will be presented using summary tables, patient data listings, and figures. Disease evaluations will be performed by investigators per the RECIST ___ criteria. Each enrolled patients will provide tumor tissues at baseline (0 week) and during treatment (4 weeks) and at disease progression. 24 pre- and treatment- biopsy pairs are planned for this study. Patients lacking pre- or treatment- biopsies will be replaced.

10.4.1 Analysis Populations

Patients who received at least 4 weeks of enzalutamide treatment will be included in the efficacy analyses. Patients who received at least one dose of enzalutamide will be included for the safety evaluation.

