3.4 Sample Size

Twenty-four (24) evaluable patients will be recruited for this study. Up to 45 patients may be consented to allow for screen failures. The 24 evaluable patients will receive serial

tumor biopsies – pre-enzalutamide treatment and at ~4 weeks on therapy. Patients will be asked to allow an optional biopsy upon progression of disease.

4. STUDY ENROLLMENT AND WITHDRAWAL:

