6.1 Study Procedures

Study Phase	Screening	Treatment				Progression	Follow-up
		1	5	9	13 [1]		
Study Week	-4 to -1	1	5	9	13 [1]	varies	varies [10]
Window (Days)	28	n/a	+/- 7	+/- 7	+/- 7	n/a	+/- 7 days
Informed Consent	x						
Eligibility	x						
Medical History	x						
Archived Tissue Collection [2]	x						
Tumor Imaging [3]	x			x			
Physical Exam	x	x	x	x	x	x	
Adverse Events	x	x	x	x	x	x	x
Concomitant Medications	x	x	x	x	x	x	
Study Drug Dispensing [4]		x		x			
Fulvestrant [9]		x	x	x	x		
Tumor Biopsy		x [5]	x			optional	
Hematology, Serum Chemistry [6]	x	x [8]	x	x	x	x	
PT/INR, PTT [11]	x		x			x	
Urine Pregnancy Test [12]	x						
Circulating Tumor Biomarkers	x	x [8]	x	x	x	x	
CTCs [7]	x	x [8]	x	x		x	
Survival & Recurrence Follow-up							x

[1] Continue every 4 weeks until progression.

[2] From primary lesion and/or metastatic sites previously biopsied. If tissue is available, archival blocks from both sites (primary and metastatic) should be collected, however, the top priority is the primary tissue.

[3] Within approximately 28 days before study entry and includes CT with contrast (unless medically contraindicated) of chest, abdomen, and pelvis. Bone assessments as clinically indicated. Thereafter, perform assessments every 8 weeks up to week 49 and then every 12 weeks thereafter until progression is documented per RECIST 1.1 or permanent treatment discontinuation. MRI is acceptable if CT not possible. Use the same testing across time.

[4] Refill every 8 weeks as long as patient remains on active treatment.

[5] Before treatment, but after eligibility determined.

[6] Hematology: hematocrit, hemoglobin, platelet count, red blood cell count, total neutrophils (absolute), white blood cell count with differential. Chemistry: albumin, alkaline phosphatase, ALT (alanine aminotransferase), AST (aspartate transaminase), blood urea nitrogen and creatinine; Ca⁺⁺, Cl⁻, K⁺, Na⁺; glucose (non-fasting), total bilirubin, total CO₂ (bicarbonate), total protein.

[7] CTCs will be collected at all participating sites, coded to remove patient identifiers, and shipped to UCCC and USC for processing as outlined in the lab manual.

[8] Only one sample is needed pretreatment (either during screening or prior to treatment on C1D1).

[9] Given IM on days 1, 15, and 28 (C2D1), and then every 4 weeks as per standard of care (SOC).

[10] 30 days after the last dose of enzalutamide or before initiation of a new antitumor treatment, whichever occurs first. May be done by telephone.

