10.5 Data Analysis Plan

10.5.1 Toxicity

The study populations will include the following:

- The Safety Population, which will include all patients who received at least 1 dose of enzalutamide;
- The Response Population, which will include all patients who received enzalutamide.

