12.2 Inadequate collection of tissues and inadequate serial samples

We anticipate inadequate specimens in up to 10% of individuals. Each investigator is determined to collect these samples and is experienced in obtaining such specimens. Handling of these tissues is routine in all institutions. All participating sites are experienced NCI designated cancer centers, and have well developed phase I and breast cancer multidisciplinary programs. All sites see a large number of new breast cancer patients per year, and have high clinical trial accruals. All of the sites lead investigators are accomplished medical oncologists with experience with phase I/II and III trials. [name] in collaboration with [name], conducted the preoperative hormone trial that established the potential importance of AR and enzalutamide in ER+ breast cancer. University of Colorado has well-established core facilities to perform Nextgen sequencing, tissue banking and processing, and CLIA certified IHC.

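### The primary clinical benefit rate has two conflicting denominators (10.4.1 and 10.5.1), and the 4-week rule in 10.4.1 biases the reported rate upward

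*Combined protocol and SAP*

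**What the plan says.** All references are to the combined protocol and SAP.

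- **10.4.1** (analysis populations): "Patients who received at least 4 weeks of enzalutamide treatment will be included in the efficacy analyses". The primary endpoint, CBR at 24 weeks, is an efficacy analysis, so this rule governs it.
- **10.5.1**: "The Response Population, which will include all patients who received enzalutamide". No minimum duration is attached.
- **10.2.1**: the design tests 10% against 30% with 24 patients, an exact binomial test and one-sided alpha 0.085, followed by "If 5 or more patients show clinical benefit the drug combination warrants further evaluation". It then notes that "patients might withdraw due to toxicity or loss to follow-up before on treatment for 24 weeks" and tabulates n from 24 down to 20, with a cut-off of 5 in every row.
- **6.1**: the first on-treatment imaging is at week 9. Footnote 3 continues imaging "until progression is documented per RECIST 1.1 or permanent treatment discontinuation".
- **10.4**: 24 biopsy pairs are planned, and "Patients lacking pre- or treatment- biopsies will be replaced".
- **3.4** attaches the paired biopsies to the 24 evaluable patients, but section 10 does not define evaluable.
- **12.2**: "We anticipate inadequate specimens in up to 10% of individuals". **12.3** would consider more enrolment only above that level, and then to reach 20 matched samples.

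**The concern.** This is a single-arm trial with one binomial decision, so the denominator is half of the primary result. The plan gives two incompatible denominators (10.4.1 and 10.5.1). Section 10.2.1 adds a third treatment of early losses by letting withdrawals reduce n.

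The 4-week rule is not neutral between them. Membership depends on an event after treatment start. Those who fail to qualify will have stopped for reasons such as progression, toxicity, death or withdrawal, and can hardly show response or 24 weeks of stable disease. Removing them lowers the denominator and leaves the numerator almost untouched. A reader comparing the reported CBR with other treatments would take it as the rate among women who start the combination, when it is the rate among those who tolerate it and stay on it for a month.

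A second question follows from the biopsy rule. Replacement is tied to tissue, not to efficacy. A patient treated for 4 weeks or more without a week-4 biopsy is replaced under 10.4 yet still meets 10.4.1. Whether she counts towards CBR is not stated.

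**Working it through.** **Step 1. Reproduce the plan's table.** Inputs from 10.2.1: p0 = 0.10, p1 = 0.30, cut-off 5. Alpha = P(X ≥ 5 | n, 0.10) and power = P(X ≥ 5 | n, 0.30), with X binomial.

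| n | alpha (plan) | alpha (computed) | power (plan) | power (computed) |
|---|---|---|---|---|
| 24 | 0.085 | 0.0851 | 0.89 | 0.8889 |
| 23 | 0.073 | 0.0731 | 0.86 | 0.8644 |
| 22 | 0.062 | 0.0621 | 0.84 | 0.8355 |
| 21 | 0.052 | 0.0522 | 0.80 | 0.8016 |
| 20 | 0.043 | 0.0432 | 0.76 | 0.7625 |

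Every row agrees at the plan's rounding.

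**Step 2. Direction of the bias.** A patient who stops permanently before week 4 has had no on-treatment scan, since the first is at week 9, and footnote 3 of 6.1 ends scanning at that point. She cannot have a scheduled scan that documents benefit. Excluding her removes a near-certain non-benefit.

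**Step 3. Effect on the reported rate.** The documents give no rate of stopping before week 4, so the number excluded is an assumption. Take 24 treated and 5 with benefit, and let k early stoppers leave the denominator: CBR = 5/(24 − k), with Clopper-Pearson 95% intervals.

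| k | CBR | exact 95% CI |
|---|---|---|
| 0 | 5/24 = 20.8% | 7.1% to 42.2% |
| 1 | 5/23 = 21.7% | 7.5% to 43.7% |
| 4 (far end) | 5/20 = 25.0% | 8.7% to 49.1% |

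The cut-off is 5 in every row of the plan's table, so the go/no-go result is the same in all three cases.

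**Step 4. Early stoppers excluded and replaced to reach 24.** Someone who stops well before week 4 would usually also lack the on-treatment biopsy, so replacement is plausible. Suppose the 10% null refers to all treated patients, a fraction f is excluded, and none of those has benefit. The null rate among analysed patients is then 0.10/(1 − f).

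- f = 0.05: 0.10/0.95 = 0.1053; P(X ≥ 5 | 24, 0.1053) = 0.101.
- f = 0.10: 0.10/0.90 = 0.1111; P(X ≥ 5 | 24, 0.1111) = 0.120.

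If the null refers to the analysed patients, the false-go rate stays at 0.085. Section 10.2.1 does not say which is meant.

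**Step 5. If treated, replaced patients stay in the denominator.** Then n can exceed 24. With 10% of patients needing replacement, 24/0.9 = 26.7, or about 27 treated. The table compares a cut-off of 5 carried over with a cut-off of 6.

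| n | alpha, R ≥ 5 | alpha, R ≥ 6 | power, R ≥ 6 |
|---|---|---|---|
| 25 | 0.098 | 0.033 | 0.807 |
| 26 | 0.112 | 0.040 | 0.837 |
| 27 | 0.127 | 0.047 | 0.864 |
| 28 | 0.142 | 0.055 | 0.887 |
| 31 | 0.193 | 0.083 | 0.937 |

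Six is the smallest cut-off that holds alpha at or below 0.085 for n = 25 to 31. At n = 32 it becomes 7.

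**The case against.** The strongest objection concerns the error rate. A reader might infer from Step 5 that the plan as written runs at an alpha of up to 0.127. The documents do not support that, for three reasons.

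- The rule of 5 or more directly follows the sentence giving n = 24 and alpha 0.085, and the table pairs each cut-off with an n. No text tells the analyst to keep 5 above 24. Applying the named test at 0.085 to 25 to 31 patients would itself give 6. The fair criticism is that no cut-off is tabulated there.
- Section 3.4 can be read as meaning that the 24 evaluable patients are those with paired biopsies and that a replaced patient falls outside them, which keeps n at 24. That reading is open, but neither population definition states it, and it would select on reaching the week-4 biopsy, which is the same kind of selection as the 4-week rule.
- The figure of 27 treats an inadequate specimen (12.2) as a missing biopsy (10.4), and these are not the same. It also sits uneasily with 12.3: at 10% inadequacy, 24 × 0.9 = 21.6 pairs remain, above the 20 that 12.3 aims for, so 12.3 would trigger no extra enrolment. Sections 12.3 and 10.4 conflict with each other.

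It can also be said that the early-stopping numbers are assumed, and that without replacement the decision does not change. Both statements are true. Neither answers the conflict between 10.4.1 and 10.5.1 or the direction of the bias.

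Finally, basing CBR on the first 24 treated would keep 5 of 24 without new cut-offs. That is workable, but it leaves later treated patients out of the primary rate.

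**Conclusion.** The point stands as a conflict of populations with an upward bias, and should be fixed. Sections 10.4.1 and 10.5.1 cannot both define the CBR denominator, and the 4-week version raises the reported rate and its interval relative to all treated patients. The direction follows from the scan schedule. The size cannot be fixed from the documents: in the illustrations it is 0.9 percentage points with one exclusion (21.7 − 20.8) and 4.2 with four (25.0 − 20.8).

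The effect on the decision is conditional. It is nil if n only shrinks from 24 to 20. The false-go rate is 0.101 or 0.120 if 5% or 10% are excluded and replaced and the 10% null describes all treated patients; it remains 0.085 if the null describes those analysed.

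The point about n above 24 is secondary. It is a gap in the plan that arises only if treated, replaced patients count towards CBR. The alphas of 0.098, 0.112 and 0.127 at n = 25, 26 and 27 show what carrying over a cut-off of 5 would do. They are not the plan's stated operating characteristics, and n = 27 is an illustration only.

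**What to change.** 1. **10.4.1 and 10.5.1:** name all patients with at least one dose of enzalutamide as the primary population for CBR and response rate. Keep the set with at least 4 weeks as a sensitivity analysis. Count anyone without documented benefit, including withdrawals and losses to follow-up, as having no clinical benefit.
2. **10.2.1:** amend the sentence that lets withdrawal or loss reduce n, so that it agrees with item 1. The rows for 20 to 23 then apply only if fewer than 24 are treated. Keep R ≥ 5 at 24 treated (alpha 0.085, power 0.89), and state R ≥ 6 for 25 to 31 treated, for example 0.033/0.81 at n = 25 and 0.047/0.86 at n = 27.
3. **10.4:** state that biopsy replacement serves the paired-tissue set only and that treated, replaced patients stay in the CBR denominator. Reconcile the 24 pairs here with the 20 matched samples in 12.3.

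The cost is wording and a few table rows, with no new data or procedures. The reported CBR may be slightly lower. Power falls from 0.89 to 0.81 if exactly 25 are treated, and recovers to 0.84, 0.86 and 0.89 at 26, 27 and 28.
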